**Table 6. Study Activities – Post-Treatment (PT) Period for Main study and Retreatment sub-study**

Activity	PT Wk 4	PT Wk 12
Physical Exam & Child-Pugh Score	As available for abstraction per SOC in the submitted redacted medical records	
Vital Signs, Weight	As available for abstraction per SOC in the submitted redacted medical records	
Concomitant Medication Assessment a	As available for abstraction per SOC in the submitted redacted medical records	
Adverse Event/Serious Adverse Event Assessment b	As available for abstraction per SOC in the submitted redacted medical records	
Hematology/Chemistry/PT/INR c	X	
HCV RNA Samples c	X	X
Pregnancy Test (urine [u]) for WOCBP only e	X (u)	X(u) d
HCV Resistance Sample c	X	X
Archive Plasma Sample c	X	X
Upload signed central lab reports evaluating clinical significance of abnormal results	X	X
Medical Records & Blood sample collection Verification Worksheet and Records Submission	X	X
For HIV co-infected subjects, CD4+ & HIV RNA results obtained locally	As available for abstraction per SOC in the submitted redacted medical records	

Wk = Week; PT D/C = Post-Treatment Discontinuation

- a Only medications taken for SAEs and for treatment of HCV will be collected after 30 days post-dosing.
- b Non-serious AEs will be collected until 30 days post dosing. All SAEs will be collected through PT WK 12. (see Section 6.1.4).
- c Collected for central laboratory processing
- d Required for WOCBP randomized to RBV arm only, or subjects of Re-treatment study who receive RBV as part of the retreatment regimen
- e If the urine pregnancy result is positive, site must confirm immediately with a serum test collected through the central laboratory

Note: Day 1 of the Post-Treatment Period will be defined as the day after the last dose of study drug.

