**Number of Subjects to be Enrolled:** up to 225 subjects**\*Applicable to Retreatment sub-study only**

**Methodology:**

**Main Study:**

This is a Phase 3b, randomized, open-label, pragmatic, multicenter study to evaluate efficacy and safety of the fixed-dose combination tablets of glecaprevir/pibrentasvir with or without RBV in NS5A-inhibitor plus sofosbuvir ± RBV-experienced, chronic HCV GT1-infected subjects. Up to 225 subjects at approximately 35 sites will be enrolled into four study arms A, B, C and D. Up to 150 non-cirrhotic subjects will be randomized in a 2:1 ratio to Arms A and B, and up to 75 subjects with compensated cirrhosis will be randomized in a 1:1 ratio to Arms C and D. Randomization will be stratified by HCV genotype 1 subtype (1b or non-1b).

Subjects without cirrhosis will be randomized 2:1 to:

Arm A: G/P 300 mg/120 mg QD for 12 weeks

Arm B: G/P 300 mg/120 mg QD for 16 weeks

Subjects with compensated cirrhosis will be randomized 1:1 to:

Arm C: G/P 300 mg/120 mg QD + weight-based RBV BID (1000 mg or 1200 mg total daily dose) for 12 weeks

Arm D: G/P 300 mg/120 mg QD for 16 weeks

Subjects who complete or prematurely discontinue the treatment will be followed for 12 weeks to monitor HCV RNA and to evaluate efficacy and the emergence and persistence of viral variants.

Scheduled visits for subjects in the planned Treatment Period consist of Day 1, Weeks 4, 8, 12 for all subjects and Week 16 for subjects in Arms B and D. During the Post-Treatment Period, subjects will have visits at Weeks 4 and 12 following completion of the Treatment Period. Efficacy and safety data will be monitored throughout the study. These data will enable assessment of virologic stopping, futility, and treatment extension criteria as described in the protocol.

---

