### **Contraception Recommendations and Pregnancy Testing**

A serum pregnancy test will be performed for all female subjects of childbearing potential at Screening. Additional urine pregnancy tests will be performed at all the visits indicated in **Table 5** and **Table 6**. Pregnancy testing is not required for females of non-childbearing potential. Determination of postmenopausal status will be made during the Screening period, based on the subject's history.

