##### **Treatment Arm Efficacy Adjustment Criteria**

Based on interim virologic data, the following adjustments will be made to individual treatment arms within the Main Study. Treatment Arm Efficacy Adjustment Criteria do not apply to the Retreatment sub-study:

1. If more than 2 subjects have confirmed on-treatment virologic failure among the first 20 non-cirrhotic subjects with available HCV viral load data across Arms A and B, the virologic failures will be examined to determine if all new enrollment into the arms should stop and if weight-based twice daily RBV (1000 mg  $<$  75 kg or 1200 mg  $\geq$  75 kg body weight total daily dose) should be added to the regimen for all future and current subjects in Arm A and Arm B, or a subset of subjects in Arms A and B. Similar analyses will continue every two weeks until all subjects in Arms A and B reach the end of treatment.
2. If more than 2 subjects have confirmed post-treatment relapse in the Post-Treatment

period among the first 20 subjects in Arm A with available post treatment HCV viral load data, the virologic failures will be examined to determine if treatment should be extended to 16 weeks for all future and current subjects in Arm A or for a subset of subjects in Arm A. Similar analyses will continue every two weeks until all subjects in Arm A reach the end of treatment.

3. If more than 2 subjects have confirmed post-treatment relapse among the first 20 subjects in Arm C with available post treatment HCV viral load data, the virologic failures will be examined to determine if treatment should be extended to 16 weeks for all future and current subjects ongoing in Arm C or for a subset of subjects in Arm C. Similar analyses will continue every two weeks until all subjects in Arm C reach the end of treatment.
4. If more than 2 subjects have confirmed on-treatment virologic failure among the first 20 subjects across Arms A, B and D, the virologic failures will be examined to determine if weight-based twice daily RBV (1000 mg <75 kg or 1200 mg  $\geq$ 75 kg body weight total daily dose) should be added for all current and future patients in Arm D or a subset of subjects in Arm D. Similar analyses will continue every two weeks until all subjects in Arms A, B and D reach the end of treatment.

Treatment failures due to non-compliance with study drugs, stopping or holding of study drugs due to adverse events, or other reasons for study drug interruptions will not count towards virologic failures.

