**\*\*\* RBV dosage form to be determined by dispensing pharmacy.**

Study drug dosing will be initiated at the Day 1 Visit in the Main study and the Retreatment sub-study if applicable. Study drug initiation does not need to be witnessed at the Day 1 visit. Based on Treatment Arm Efficacy Adjustment criteria in Section 5.4.1.1, if virologic futility criteria are met, RBV dosing may be added to already ongoing or new initiation of G/P dosing in Arms A, B, or D.

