#### **6.1.6                    Pregnancy**

Female subjects randomized or assigned to non-RBV containing regimen in Main study or Retreatment sub-study should avoid pregnancy starting with screening and through 30 days after completion of study drug. Female subjects randomized or assigned to RBV containing regimen in Main study or Retreatment sub-study should avoid pregnancy starting with Screening and through 6 months after completion of study drug (or as per

local RBV label). Male subjects randomized to G/P in Main study or receiving G/P plus SOF in Retreatment sub-study and their partners should avoid pregnancy starting with screening and through 30 days after completion of study drug. Male subjects randomized or assigned to RBV containing regimen in Main study or Retreatment sub-study and their partners should avoid pregnancy starting with Screening and through 7 months after completion of study drug (or as per local RBV label).

Pregnancy in a study subject must be reported to the sponsor within 1 working day of the site becoming aware of the pregnancy and should be reported to the Ribavirin Pregnancy Registry, as applicable. Administration of G/P in Main study or G/P plus SOF in Retreatment sub-study may be continued at the investigator's discretion after discussion with the subject, if the benefit of continuing therapy is felt to outweigh the risk (Section 5.4.1). If a subject is discontinued, the subject will be monitored for SVR in the Post-Treatment Period as described in Section 5.1.3.

Information regarding a pregnancy occurrence in a study subject and the outcome of the pregnancy will be collected for pregnancies occurring up to 30 days after the end of treatment for subjects receiving a non-RBV containing regimen or up to 6 months (female subjects) or 7 months (male subjects) after the end of treatment for subjects receiving a RBV containing regimen.

Pregnancy in a study subject is not considered an adverse event. However, the medical outcome of an elective or spontaneous abortion, stillbirth or congenital anomaly is considered a serious adverse event and must be reported to the sponsor within 24 hours of the site becoming aware of the event.

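### Table 6 footnote d ties the Main-study PT Week 12 pregnancy test to randomisation to RBV, so a woman in Arm A, B or D who is given RBV later has no required test at that visit (minor, contingent)

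*Protocol*

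**What the plan says.** **Testing schedule.** Table 6 lists a urine pregnancy test for women of childbearing potential (WOCBP) at PT Week 4 with no RBV condition, and at PT Week 12 subject to footnote d: "Required for WOCBP randomized to RBV arm only, or subjects of Re-treatment study who receive RBV as part of the retreatment regimen". The pregnancy-testing paragraph of Section 5.3.1.1 sets no schedule of its own: "Additional urine pregnancy tests will be performed at all the visits indicated in" Tables 5 and 6.

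**Who is randomised to RBV.** In the Synopsis and Section 5.1, one Main-study arm contains RBV at randomisation: "Arm C: G/P 300 mg/120 mg QD + weight-based RBV BID (1000 mg or 1200 mg total daily dose) for 12 weeks". Arms A, B and D are G/P alone.

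**Who may receive RBV later.** Section 5.4.1.1, criterion 1, opens with "If more than 2 subjects have confirmed on-treatment virologic failure among the first 20 non-cirrhotic subjects" across Arms A and B. The failures are then examined to decide whether RBV "should be added to the regimen for all future and current subjects in Arm A and Arm B", or to a subset of them. Criterion 4 does the same for Arm D, where RBV "should be added for all current and future patients in Arm D or a subset of subjects in Arm D". Section 5.5.5 confirms that "RBV dosing may be added to already ongoing or new initiation of G/P dosing in Arms A, B, or D".

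**Pregnancy rules elsewhere.** Section 6.1.6 states: "Female subjects randomized or assigned to RBV containing regimen in Main study or Retreatment sub-study should avoid pregnancy starting with Screening and through 6 months". The period is counted from the end of study drug, or is as the local RBV label directs. The same section collects pregnancy information for 6 months in women who receive an RBV-containing regimen. Section 3.6 describes RBV as a teratogen, pregnancy category X.

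**The concern.** Footnote d applies two different tests of exposure in one sentence. For the retreatment sub-study it asks whether the woman receives RBV; for the Main study it asks whether she was randomised to it. The two coincide in the Main study as long as only Arm C takes RBV. They separate once the protocol's own adjustment rules put RBV into Arm A, B or D for women randomised before the change.

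At stake is a safety check, not an analysis. PT Week 12 is the last scheduled visit and falls inside the 6-month period in which a woman exposed to RBV should avoid pregnancy. The protocol requires the test there for women with the same exposure in Arm C and in the sub-study. The schedule should cover a treatment change that the protocol itself provides for.

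**Working it through.** No probability or sample-size formula applies. The check compares the sections and counts the scheduled tests.

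**Step 1: does footnote d reach the woman in question?** Take a WOCBP randomised to Arm A on G/P alone who is given RBV during treatment under criterion 1.
- Main-study condition (randomised to the RBV arm): not met, because her randomised arm was G/P alone. The word *only* in the footnote shuts out a looser reading.
- Sub-study condition (receives RBV on retreatment): not met, because she is in the Main study.

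The same holds for Arm B under criterion 1 and Arm D under criterion 4.

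**Step 2: does another section supply the test?**

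| Place | What it does for her |
|---|---|
| Table 5 | Urine tests at Day 1 and every on-treatment visit, in any arm |
| Table 6, PT Week 4 | Urine test, in any arm |
| 5.3.1.1, pregnancy testing | Refers back to Tables 5 and 6; adds no test |
| 5.3.1.1, clinical laboratory tests | Describes the listed samples as a minimum: permits more, requires none |
| 6.1.6 | Avoidance period, pregnancy reporting and collection; no testing rule |
| Appendix C | Contraception while on RBV and for 6 months after stopping it; no testing rule |

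Nothing closes the gap at PT Week 12.

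**Step 3: count the scheduled urine tests** (treatment completed as planned).
- Arm A with RBV added: Day 1, Weeks 4, 8 and 12, PT Week 4 = 5
- Arm C: the same five plus PT Week 12 = 6
- Arm B or D with RBV added: Day 1, Weeks 4, 8, 12 and 16, PT Week 4 = 6
- Retreatment sub-study with RBV: the same six plus PT Week 12 = 7

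The difference is one test in each pairing (6 − 5 and 7 − 6).

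**Step 4: date the last required test.** PT Week 4 is nominally day 4 × 7 = 28 after the last dose, and PT Week 12 is day 12 × 7 = 84. Her last required test therefore comes 84 − 28 = 56 days earlier than that of a woman in Arm C. This assumes that RBV and G/P stop on the same day. Taking 6 months as about 26 weeks, about 26 − 4 = 22 weeks of the avoidance period follow her last required test, against 26 − 12 = 14 weeks in Arm C.

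**Step 5: which standard does the protocol use elsewhere?** Section 6.1.6 goes by randomised *or assigned* for avoidance and by *receiving* for collection. The sub-study half of footnote d goes by receipt. The Main-study half of footnote d is the narrower one.

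**The case against.** The best defence is that Tables 5 and 6 describe the planned regimens and would be updated if an adjustment were adopted. Table 5 footnote i follows the same habit: it ties the Week 16 visit to Arms B and D and the sub-study, without naming an Arm A or C extended under criteria 2 and 3. The protocol also uses *randomized* as shorthand for the regimen in Exclusion Criterion 1 (Section 5.2.2) and in Appendix C, and Section 8.1 analyses subjects by final treatment arm assignment. If RBV were added to a whole arm, that arm could fairly be called an RBV arm, and a woman randomised to it afterwards would meet the footnote.

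Much of this stands, and it keeps the point small. It does not settle the case of a subset of current subjects: their arm has not become an RBV arm, and no text says that the schedule changes with their regimen.

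The other safeguards also stand. The on-treatment tests, the PT Week 4 test, contraception, the avoidance period and pregnancy reporting all still apply. Even Arm C has no scheduled test after PT Week 12, so this test is not the main protection. The consent form and subject information, which are not available here, may say more.

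Two stronger readings are tempting:
- A reader might infer that women given added RBV would go without pregnancy monitoring. The list above shows otherwise.
- A reader might want a probability that RBV is added, worked out from the MAGELLAN-1 failure rates in Section 3.4. The documents do not support one for this version. Section 3.4 reports 130 patients already screened and Section 8.2 calls the study ongoing, so the look at the first 20 subjects may have passed. Meeting a criterion also leads only to a review, with the data monitoring committee of Section 11.0, and adds no RBV by itself.

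**Conclusion.** The point holds as a minor, contingent inconsistency. On its literal wording, footnote d omits the PT Week 12 urine test for a WOCBP already in Arm A, B or D who is then given RBV, while Section 6.1.6 treats her as exposed for 6 months. The size is one test per affected woman, with her last required test at about day 28 instead of day 84. These are counts and dates; they do not measure risk.

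The conclusion rests on a literal reading of *randomized*, which is firmest where RBV goes to a subset of an arm and weaker where it goes to the whole arm. It also needs three things to happen: a criterion is met, the review decides for RBV, and a WOCBP is among those who receive it. The number affected is not given and may be zero. No efficacy estimate, confidence interval, sample size or error rate is touched.

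**What to change.** Reword Table 6 footnote d along these lines: *Required for WOCBP randomized or assigned to, or who received, an RBV-containing regimen in the Main study or Retreatment sub-study.* This matches Section 6.1.6 and puts both halves of the footnote on the same basis.

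Optionally, align the randomisation-based wording in Exclusion Criterion 1 (Section 5.2.2) and in Appendix C at the same time, so that the terms agree throughout.

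The cost is one reworded footnote and one urine test at a visit that already takes place, only for WOCBP given added RBV. Nothing changes for women who never take RBV.

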### 5.3.1.1 Study Procedures

## **Informed Consent**

Signed study-specific informed consent will be obtained from the subject before any study procedures are performed. Subjects who failed treatment in the Main study and elect participation in the Retreatment sub-study require additional informed consent before any procedure of the Retreatment sub-study is performed.

## Medical History, Physical Examinations, Vital Signs and Weight, Clinical Assessment of Hepatic Decompensation

All original clinic notes, telephone notes, locally available safety labs/evaluations and/or diagnostic tests or health screenings collected prior to, during and post HCV treatment period will be submitted for chart data abstraction to identify and abstract medical history, vital signs, weight (and height historically) and physical examinations that were collected as part of standard of care practice. The medical history listing, assessment for historical/current hepatic decompensation and Child Pugh score examination procedures will be updated at the standard of care visit where study informed consent is obtained. The site will submit medical records created as part of screening/informed consent, as well as medical records available in the site medical records system, for up to 24 months prior to the study screening. Older records to document key medical history and liver disease/HCV treatment history will also be submitted for centralized abstraction.

## Child-Pugh Score and Category

The Child-Pugh score uses five clinical measures of liver disease (3 laboratory parameters and 2 clinical assessments). Child-Pugh score will be determined at the visits indicated in **Table 5 and Table 6**.

**Table 7. Child-Pugh Score for Classification of Severity of Cirrhosis**

Parameter	Points Assigned for Observed Findings		
	1	2	3
Total bilirubin, $\mu\text{mol/L}$ ( $\text{mg/dL}$ )	$< 34.2 (< 2)$	$34.2 - 51.3 (2 - 3)$	$> 51.3 (> 3)$
Serum albumin, $\text{g/L}$ ( $\text{g/dL}$ )	$> 35 (> 3.5)$	$28 - 35 (2.8 - 3.5)$	$< 28 (< 2.8)$
INR	$< 1.7$	$1.7 - 2.3$	$> 2.3$
Ascites*	None	Slight	Moderate to severe
Hepatic encephalopathy**	None	Grade 1 or 2 (or suppressed with medication)	Grade 3 or 4 or refractory

\* None; Slight ascites = Ascites detectable only by ultrasound examination; Moderate ascites = Ascites manifested by moderate symmetrical distension of the abdomen; Severe ascites = Large or gross ascites with marked abdominal distension.

\*\* Grade 0: normal consciousness, personality, neurological examination, electroencephalogram; Grade 1: restless, sleep disturbed, irritable/agitated, tremor, impaired handwriting, 5 cps waves; Grade 2: lethargic, time-disoriented, inappropriate behavior, asterixis, ataxia, slow triphasic waves; Grade 3: somnolent, stuporous, place-disoriented, hyperactive reflexes, rigidity, slower waves; Grade 4: unarousable coma, no personality/behavior, decerebrate, slow 2 to 3 cps delta activity.

## Clinical Laboratory Tests

A central laboratory will be utilized to process and provide results for the clinical laboratory tests. Samples will be obtained at a minimum for the central laboratory tests outlined in **Table 8** at the visits indicated in **Table 5** and **Table 6**.

Instructions regarding the collection, processing, and shipping of these samples will be provided by the central laboratory chosen for this study.

**Table 8. Clinical Laboratory Tests**

Hematology	Clinical Chemistry
White Blood Cell (WBC) count	Albumin
Red Blood Cell (RBC) count	Alkaline phosphatase
Hemoglobin	Alanine aminotransferase (ALT)
Hematocrit	Aspartate aminotransferase (AST)
Platelets	Bilirubin, Direct
Neutrophils	Bilirubin, Indirect
Lymphocytes	Bilirubin, Total
Monocytes	Blood Urea Nitrogen (BUN)
Eosinophils	Calcium
Basophils	Carbon Dioxide
Bands, if detected	Chloride
Prothrombin Time (PT)	Cholesterol
INR	Creatinine
Other Tests	
Urine and Serum Human Chorionic Gonadotropin (hCG) for females (pregnancy)	Glucose
HCV RNA	Phosphorus
HCV genotype and subtype	Potassium
HBsAg, Hep B Core Ab-Total, Hep B Surface Ab	Sodium
reflex HBV DNA a	Total protein
HIV 1-2 b	Uric Acid
APRI and Fibrotest	eGFR by MDRD

aIf HBsAg neg, Hep B Core AB-Total positive at ScreeningbOnly required for subjects without historical positive test result for HIV Ab

For any laboratory test value outside the reference range that the investigator considers to be clinically significant:

- The investigator will repeat the test through the central laboratory to verify the out-of-range value.
- The investigator will follow the out-of-range value to a satisfactory clinical resolution.
- A laboratory test value that requires a subject to be discontinued from the study, a dose modification of RBV, or requires a subject to receive treatment will be recorded as an adverse event.

The management of laboratory abnormalities that may occur during the study is described in Section 6.1.6

### **Contraception Recommendations and Pregnancy Testing**

A serum pregnancy test will be performed for all female subjects of childbearing potential at Screening. Additional urine pregnancy tests will be performed at all the visits indicated in **Table 5** and **Table 6**. Pregnancy testing is not required for females of non-childbearing potential. Determination of postmenopausal status will be made during the Screening period, based on the subject's history.

### **Concomitant Medication Assessment**

Excluding the medications and substances listed in Table 4, use of medications (prescription or over-the-counter, including vitamins, herbal supplements, and vaccines) from the time of signing the consent, through the Treatment Period, and 30 days after study drugs are stopped must be recorded in the medical record according to the local standard of care. Only medications taken for SAEs and for treatment of HCV will be abstracted from the submitted medical records 30 days after study drugs are stopped as indicated in **Table 6** (Post-Treatment Period). The concomitant medication listing will be updated in the standard of care medical record at the time of informed consent. All original clinic notes

and telephone notes collected prior to, during, and post HCV treatment period will be submitted for chart data abstraction to identify and abstract concomitant medication(s) that were prescribed as part of standard of care practice.

